**Specific Aim 3:**

**To evaluate the extent to which a data-driven HOT management protocol can improve growth and respiratory outcomes.**

*We hypothesize that RHO utilization will not increase rates of respiratory-related re-hospitalizations and ED visits, and will not impair growth compared to standard oxygen management protocols.*

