#### **4.e. Definition of Primary and Secondary Outcomes/Endpoints**

Primary measures: (a) Total duration of home oxygen therapy (HOT) from the first outpatient pulmonary appointment to discontinuation of supplemental O2; and (b) Parent quality of life, assessed by differences in the post-weaning PedsQL baseline.

Secondary measures: (a) Number of rehospitalizations and emergency department visits from 1st clinic visit through 6 months after discontinuation of HOT; (b) Change in weight and weight-for-length z-score from 1st clinic visit to 6 months after discontinuation of HOT; and (c) For patients who will receive a sleep study, percent time below designated O2 saturation thresholds (<96%, <93%, and < 90%) will be calculated from both RHO and from the polysomnogram data. The number of desaturation events (defined as saturation drops below 90% for >10 seconds and > 20 seconds) will also be analyzed.

Duration of HOT was chosen as a primary outcome since it is the primary driver of caregiver emotional and financial health for families of infants on HOT. This outcome was driven by input from families themselves, through a process of including important stakeholders in the protocol development process. The PedsQL was chosen as an additional primary outcome because it is validated, accurate scale in which scores correlate with maternal psychiatric symptoms, poor child health, poor child adjustment, and increased child hospitalizations.

This protocol focuses on patient-centered outcomes that may demonstrate non-inferiority from a medical safety perspective, but may improve quality of life. While families place a priority on treatment strategies that optimize health, when there are multiple choices without a clear medically superior choice, then the impact of specific treatment choices on quality of life will help drive decision-making.

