**Table 1.**  
**O2 WEANING PARAMETERS**

	STANDARD OXYGEN MANAGEMENT ARM	CpOx OXYGEN MANAGEMENT ARM
CRITERIA FOR INCREASING O2 FLOW RATE	INABILITY TO MAINTAIN O2 SAT >93% AT PATIENT'S CURRENT O2 LEVEL FOR 20 MINUTES IN CLINIC VISIT CHALLENGE	INABILITY TO MAINTAIN O2 SAT >93% FOR >95% OF RECORDED TIME
CRITERIA FOR MAINTAINING CURRENT O2 FLOW RATE	ABILITY TO MAINTAIN O2 SAT >93% AT PATIENT'S CURRENT O2 BUT UNABLE TO MAINTAIN O2 SAT >93% AT WEANED FLOW RATE FOR 20 MINUTES IN CLINIC VISIT CHALLENGE	ABILITY TO MAINTAIN O2 SAT >93% FOR >=95% OF RECORDED TIME BUT UNABLE TO MAINTAIN O2 SAT >96% FOR >=95% OF RECORDED TIME
CRITERIA FOR WEANING O2 FLOW RATE	ABILITY TO MAINTAIN O2 SAT >96% AT WEANED FLOW RATE FOR 20 MINUTES IN CLINIC VISIT CHALLENGE	ABILITY TO MAINTAIN O2 SAT > 96% FOR >=95% OF RECORDED TIME

\* Clinic pass and fail will be determined per clinic assessment of oximeter alarms.

\*\* CpOx pass and fail will be determined by assessment of recorded oximetry. A minimum of 4 days of data, with a minimum of 8 hours per day, will be required for analysis to make any wean.

For infants in both arms, O2 weaning will proceed, when allowable per weaning criteria in the protocol, in 50% increments to a minimum of 125 cc/min. (For example, flow rate of 500 cc/min will be decreased to 250 cc/min, and 250 cc/min will be decreased to 125 cc/min.) Once infants achieve flow rates of 125 cc/min (or if they are discharged home from NICU on <125 cc/min), the next weaning step will be to room air during the day and nocturnal O2 only at a flow rate of 125 cc/min.

When infants in arm A have weaned to the final stage before discontinuation (O2 flow rate <= 125 cc/min, utilized only at night), they will be scheduled for an overnight polysomnography (PSG). These infants will have overnight recording with the Masimo Rad-8 pulse oximeter and serial data recorder on the nights prior to and during the PSG. Final decision regarding safe discontinuation of supplemental O2 therapy will be based on O2 saturation and growth outcomes; infants who do not meet criteria on the first PSG will remain on overnight O2 supplementation and repeat the PSG monthly until they pass.

To determine “Pass” of PSG or to determine ability to wean versus hold on current therapy versus escalate support, strict protocols to analyze O2 saturation status will be followed:

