**d. Statistical Power and Sample Considerations**

*Analyses for Aim 1:*

Aim 1: To evaluate the effects of a data-driven HOT management protocol on parent(s) quality of life.	Hypothesis 1.1: Parents of patients weaned from HOT using a data-driven management protocol will have improved quality of life compared to their status at time of NICU discharge compared to patients weaned using the current standard HOT management protocol.
--	--

For the impact of oxygen management protocol on the family's emotional health, we will use the PedsQL. We are performing these scales at the beginning of the outpatient HOT management process, to establish a baseline, and then will repeat these measures at the end of the HOT weaning process (6 months after discontinuation of HOT). We will test the association of oxygen management protocol with change in each measure using the Student's *t*-test to analyze the difference between intervention groups. Multivariate linear regression models will adjust for potential confounding variables, including parent and medical attributes.

Power calculation for hypothesis 1.1:

Power calculations are based on the primary analyses (t-test). A sample size of 130 will give 80% power, with 0.05 two-sided type I error rate, to detect a 20% absolute difference in emotional role limitation on the PedsQL, which we consider to be clinically significant.

*Analyses for Aim 2:*

Aim 2: To evaluate the impact of a data-driven HOT management protocol on duration of HOT.	Hypothesis 2.1: A data-driven HOT protocol will shorten duration of HOT therapy compared to the current standard HOT management protocol.
---	--

For the primary outcome, duration of HOT, the interval from date of first outpatient clinic visit/enrollment to discontinuation of HOT will be determined. Mean duration of HOT between the two groups will be compared.

Based on our experience weaning over 130 premature infants from O2, we expect the mean duration of HOT in our standard treatment group (clinic-based weaning) to be 144+/-66 days, and we anticipate that RHO weaning strategies will decrease the median duration by 25% (36 days) to 108 days. A total sample of 98 infants per group provides 97% power to detect this effect of the RHO strategy (two-tailed, alpha=0.05, see Table 2).

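### If weight is analysed as raw change, the growth outcome counts against an RHO arm that succeeds, because its window ends 6 months after each infant's own weaning

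*Combined protocol and SAP*

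**What the plan says.** Section 4.e lists as a secondary measure "Change in weight and weight-for-length z-score from" the first "clinic visit to 6 months after discontinuation of HOT". The post-wean visit text in section 4f makes the 6-month post-wean visit the last growth measurement and the end of participation.

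Section 5d starts the clock for the primary outcome at the same visit: "the interval from date of first outpatient clinic visit/enrollment to discontinuation of HOT will be determined". For the size of the effect it says "we expect the mean duration of HOT in our standard treatment group (clinic-based weaning) to be 144+/-66 days" and expects RHO to "decrease the median duration by 25% (36 days) to 108 days".

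Growth has a safety role. Specific Aim 3 in the abstract hypothesises that RHO "will not impair growth compared to standard oxygen management protocols", and the closing rationale of section 4.e uses growth to confirm that the weaning strategies are safe over the longer term. Hypothesis 3.1 in section 5d goes further and expects better growth with RHO.

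Sections 5c and 5d give no analysis for growth: no test, margin, SD, rate per day, common time point or age adjustment. The regression adjustment in section 5d is described for quality of life only. Section 4f names WHO for growth parameters at the monthly visits but does not say that weight is analysed as a z-score.

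**The concern.** Infants gain weight as they age. Here the date of the final weight is set by when oxygen stops, which is what RHO is meant to bring forward. Randomisation does not protect the comparison, because the difference in window length arises after randomisation and through the treatment.

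The wording of the outcome can be read in two ways: raw weight plus a weight-for-length z-score, or z-scores for both. On the first reading, the more RHO shortens oxygen therapy, the worse it looks on weight gain, even if both arms grow identically. A safety outcome could then show harm that is not there, or hide the growth benefit that Hypothesis 3.1 expects.

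**Working it through.** **Inputs from the documents.** Mean HOT duration is 144 days in the standard arm, with SD 66. The planned reduction is 36 days, to 108. (Section 5d mixes mean and median here; the figures are treated as means.) There are 98 enrolled per arm. The Table 2 caption gives 85% completing, and 0.85 × 98 ≈ 83.

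**Assumed inputs, not in the documents.** Weight gain at the relevant age is 8 to 15 g/day, linear and equal in both arms. The SD of weight change at a fixed window (the residual SD) is 0.8 to 1.2 kg, with 1.0 as the central value. The test is a two-sided 0.05 t-test, since the plan names none for growth.

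**The plan's own figure.** Section 5d states that "A total sample of 98 infants per group provides 97% power to detect this effect of the RHO strategy". A two-sample calculation with 98 per arm, difference 36 and SD 66 gives 0.967, which agrees. With 83 per arm it gives 0.94, so the stated 97% does not include the attrition named in the caption. The planned effect that makes the windows unequal is thus one the trial is well powered to find.

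**Windows.** With 6 months ≈ 183 days:
- Standard: 144 + 183 = 327 days.
- RHO: 108 + 183 = 291 days.
- Gap: 36 days, and 36/327 = 11%.

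**Apparent deficit on raw weight with no growth effect** = 36 × daily gain.

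**Total SD.** The windows vary between infants with SD 66 days, and this adds 66 × daily gain to the spread of weight change. Total SD = √(residual² + (66 × gain)²).

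**Chance of a significant deficit** comes from the noncentral t with 164 degrees of freedom and noncentrality = deficit / (total SD × √(2/83)). For 8 g/day and residual SD 1.0 kg this is 0.288 / (1.131 × 0.155) = 1.64. For 15 g/day it is 0.540 / (1.407 × 0.155) = 2.47.

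| Gain (g/day) | Deficit (kg) | 66 × gain (kg) | Total SD at residual 1.0 (kg) | Chance, residual 0.8 | residual 1.0 | residual 1.2 |
|---|---|---|---|---|---|---|
| 8 | 0.288 | 0.528 | 1.131 | 49% | 37% | 29% |
| 10 | 0.360 | 0.660 | 1.198 | 60% | 49% | 39% |
| 12 | 0.432 | 0.792 | 1.276 | 69% | 58% | 49% |
| 15 | 0.540 | 0.990 | 1.407 | 78% | 69% | 60% |

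A simulation with individual windows gave 46% at 10 g/day and 57% at 12 g/day (residual SD 1.0 kg), close to the table. With one common window for both arms, the simulated chance of a significant result against RHO was 2.3% to 2.6%, against a nominal 2.5%.

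**Z-scores.** A weight-for-length z-score is standardised for length, and a weight-for-age z-score for age. The grams-per-day arithmetic applies to neither. Only a real trend in z-score over time would leave a difference between arms measured at different ages.

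**The case against.** The strongest reply is that the z-score label in section 4.e may govern both terms, and the WHO reference in section 4f fits that reading. This stands. A reader might infer that the whole growth outcome will make RHO look harmful, but the documents do not support that: one component is explicitly a z-score and the other may be.

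A reader might also put the chance of a false signal at 45% to 93%, by treating 1.0 kg as the total SD of weight change. That conflicts with the plan's 66-day spread. At 15 g/day the spread alone contributes 0.99 kg, which leaves √(1.0² − 0.99²) = 0.14 kg for every other source of variation. The spread has to be added, as in the table.

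A third inference is that slow growers in Arm A stay on oxygen longer and so are weighed later, because the text below Table 1 bases the final decision on "saturation and growth outcomes; infants who do not meet criteria on the first PSG will remain on overnight" oxygen. That mechanism is speculative. No growth threshold is stated, neither column of Table 1 contains a growth condition, and the PSG pass definition uses only saturation and recording time. The mention of growth and the pass definition should be reconciled, but the present point does not depend on it.

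Finally, the post-wean anchor is deliberate. Section 4.e explains that outcomes 6 months after stopping were chosen so that later harm is not missed. That is a good reason to keep the assessment, but it does not justify comparing raw weight change over windows of different length.

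**Conclusion.** The point holds in conditional form. The window depends on the primary outcome, is about 36 days (11%) shorter in the RHO arm under the plan's own effect, and is not corrected anywhere in the analysis plan. If weight is analysed as raw change, a successful RHO arm would show 0.29 to 0.54 kg less gain with no true effect on growth. That would be significant in about 37% to 69% of trials at a residual SD of 1.0 kg, and in 29% to 78% over 0.8 to 1.2 kg. The window lengths rest on the documents. The kilograms and percentages rest on assumed growth rates, SDs and test.

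The weight-for-length z-score is not affected by this arithmetic, and the problem largely disappears if weight is also a z-score. As this is a secondary outcome with a safety role, and the direction of the bias is predictable, the wording should be settled before analysis.

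**What to change.** 1. In section 4.e, define the weight component as weight-for-age z-score at corrected age, alongside the weight-for-length z-score.
2. In section 5, state the growth analysis: both z-scores compared between arms, adjusted for the first-visit value.
3. Keep the 6-month post-wean z-scores, since that anchor was chosen to detect later harm.
4. Add a comparison at a common time since the first visit, from a mixed model on the growth measurements taken monthly before weaning and at 1 and 6 months after. About 6 months from the first visit suits, because every completer is followed for HOT duration plus 6 months. A later time such as 10 months (304 days) does not. With normal windows and SD 66, (304 − 291)/66 = 0.20 puts about 58% of the RHO arm past their final visit, and (304 − 327)/66 = −0.35 puts about 36% of the standard arm there, so extrapolation would be unequal between arms.
5. Report raw weight change to 6 months post-wean as descriptive only.

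The cost is outcome and analysis wording, with no new measurements. There are two downsides. The common-time value is partly model-based, because growth visits after weaning are sparse. The arms will also differ in time off oxygen at that point, by up to about 36 days on average under the planned effect, so it should be read together with the post-wean result.

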#### **4f. Data Collection Methods, Assessments and Schedule**

Each enrolled patient will receive a coded deidentifier, which will be used in a RedCap database to preserve confidentiality of all data linked to that patient.

##### **Informed Consent:**

Consent for this study at BCH will be obtained by the site PI or study team.

Consent will be obtained at the first study visit at all sites. Adequate time will be allowed between the review of the consent form and the signing of the consent form to allow families to decide on their participation. We will gauge the parents' level of understanding by asking them questions about the various elements of the consent. Significant new findings during the course of the research would require changes to the informed consent document. Subjects would be re-consented with the new approved

consent form at their next study visit, prior to any procedures being performed. Because at BCH we feel it will be important for other healthcare providers to know if the child is participating in this study, the consent forms will be placed in the subjects BCH medical record.

ARMA										Follow-up					
Study Period		Baseline (Initial Visit)					Follow-up								
Visit	V0	V1	–	V2	–	V3	–	V4	–	V5	1 mo post wean	–	3 mo post wean	–	6 mo post wean (Final visit)
Consent	X														
Eligibility Criteria	X														
NICU Discharge Summary	X														
Clinic O2 Setting	X	X	X	X	X	X	X	X	X						
PedsQL	X	X	X	X	X	X	X	X	X			X			
Growth Assessment	X	X	X	X	X	X	X	X	X					X	
PSG															
AE/ED/Rehospitalizations			X	X	X	X	X	X	X			X			X
Nutrition Assessment	X	X	X	X	X	X	X	X	X						X

ARMB										Follow-up					
Study Period		Baseline (Initial Visit)					Follow-up								
Visit	V0	V1	–	V2	–	V3	–	V4	–	V5	1 mo post wean	–	3 mo post wean	–	6 mo post wean (Final visit)
Consent	X														
Eligibility Criteria	X														
NICU Discharge Summary	X														
Clinic O2 setting/Home Oximetry Data	X	X	X	X	X	X	X	X	X	X					
PedsQL	X	X	X	X	X	X	X	X	X	X			X		
Growth Assessment	X	X	X	X	X	X	X	X	X	X					X
AE/ED/Rehospitalizations		X	X	X	X	X	X	X	X	X			X		X
Nutrition Assessment	X	X	X	X	X	X	X	X	X	X					X
Home Ox Feasibility Questionnaire*											X*				

\*Home Oximetry Feasibility Questionnaire will be collected at the 1 month post wean follow-up visit. However, If a patient is missed or lost to follow-up, research staff may call the family to obtain this information as soon as possible before their last visit.

**- Baseline Visit ( First Initial Visit): V0**  
**(For all patients in ARM A and ARM B )**

After confirming eligibility and obtaining the consent form, growth parameters, nutrition notes, NICU discharge summary, demographics and PedsQL survey will be obtained at this visit.

Medical records will be transferred to UMass using methods to ensure data safety, for abstraction by study staff. [name] will train study staff in abstraction of medical records.

Each site PIs will perform the baseline growth assessment and perform randomization at time of enrollment. We will perform block randomization to ensure equal distribution within each site.

Study staff at BCH will ask parents to complete a PedsQL at the initial (baseline) clinic visit. Research staff at BCH will hand the questionnaire to the parent for self-report in order to minimize response bias and standardize methods. If for some reason the PedsQL is not completed in clinic, staff at BCH or UMass will contact the family to complete the survey over the phone shortly after the visit. Growth and nutrition information from this visit will also be recorded.

At the end of the visit, contact information will be confirmed, and the parent will be reminded about the next planned phone/clinic visit and interview.

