## **4. Design and Methods**

### ***4a. Study Design***

We plan a prospective, multicenter, randomized trial of premature infants who require HOT. We will follow infants, beginning at the time of their first outpatient pediatric pulmonary appointment and continuing until 6 months from discontinuation of HOT. Duration of HOT therapy for each arm of the study will be documented by each site investigator. Questionnaires throughout the HOT managing process and after oxygen discontinuation will assess the impact of each HOT managing process on the parent quality of life. Growth assessments throughout of the HOT managing process and after oxygen discontinuation will track safety of both protocols. Similarly, assessment of health-care utilization (respiratory-related emergency department visits or rehospitalizations) at 6 months after discontinuation of HOT will track safety as well.

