#### **4c. Recruitment Methods**

This is a multi-center study. [name] is the Principal Investigator at University of Massachusetts Medical Center (UMass)).UMass Medical Center will act as the coordinating center. The other sites include, Boston Children's Hospital (PI: [name]) Baystate Medical Center (PI: [name]), UConn Medical Center (PI: [name]), University of Vermont Medical Center (PI. [name]), Dartmouth-Hitchcock Medical Center (PI: [name] [name]), Tufts Medical Center (PI: [name]), Boston Children's Hospital Physicians (PI: [name]) and Kentucky Children's Hospital, University of Kentucky (PI: [name] [name])

At BCH, potential eligible patients will be identified through one of two potential mechanisms: (1) identification of infants approaching readiness for discharge who will require supplemental home oxygen therapy (HOT) from Brigham and Women's Hospital (BWH) NICU or Beth Israel Deaconess Hospital (BIDMC) NICU or (2) identification of infants who present at their first outpatient appointment to the Center for Healthy Infant Lung Development (CHILD Clinic).

The site PI will review the NICU census at BWH and BIDMC once per week to identify infants who are approaching discharge and will require HOT, and to determine if there are contraindications to approaching families. They will then provide information about the study to parents in the NICU.

For infants who are eligible but not able to be approached due to logistics, or infants who are eligible but were discharged from other NICUs, the first provision of information will be at the first CHILD Clinic visit in their clinic room.

We will provide fliers to local referring NICUs to distribute to patients who will be discharged home on oxygen. These fliers will include contact information for study staff so that families may proactively ask questions or learn more about the study prior to their first clinic visit.

Subject recruitment will be performed by a team of research assistants in the study.

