### **Study Procedures:**

- **PedsQL:**

The PedsQL consists of 36 items that assess eight health domains labeled physical functioning, role limitations due to physical or emotional health, bodily pain, general health, vitality, social functioning and mental health. For the purpose of reporting results, the raw scores rating each health domain are transformed to a score that can range from 0 to 100, with higher scores reflecting better functioning. Considerable information about the validity and reliability of this measure is available. We have performed a preliminary review of the PedsQL with our Parent Advisory Board, and will work with them to augment these measures and ensure that planned measures adequately address the parent perspective.

- **Oxygen Management Protocols**

At time of enrollment, infants will be randomized to one of the oxygen management protocols (utilization of RHO or routine care). Infants randomized to utilization of RHO will receive a Masimo Rad-8 pulse oximeter and serial data recorder to record HbO2 SAT and heart rate, and will receive instruction regarding when to record the infant and how to send in data.

- **Home Pulse Oximeter Recording Procedures**

The recording system we used for prior studies and plan to use for this study is the Masimo Rad-8 pulse oximeter with an attached data recorder and removable memory card with ample capacity (2 GB) to store the continuous data recorded for each infant. The oximeter will be set for the minimum (2 sec) averaging time. Since the study oximeter will not be used as a monitor but rather as a (**continuous**) recorder, it will be preset in the sleep lab mode; there will be alerts for “probe off” and “low battery,” but no alarms for HbO2 SAT or heart rate, and no visual displays of HbO2 SAT. ***Infants will utilize their clinically-provided monitor as determined by their primary clinical team to serve as their monitor.***

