**c. Data Analysis Plan**

We employed a block randomization design for each site to ensure balanced distribution of treatment groups. Baseline characteristics and the duration of the O2 management in RHO and control groups will be compared using the independent sample test for continuous measures and the  $\chi^2$  test for categorical measures. To compare the oximetry in the sleep study and the home recording studies, we will use generalized estimating equation (GEE) gamma regression models for longitudinal count data. Gamma regression models are appropriate for highly skewed measurement or count outcome data, and exponentiating the regression parameters from these models gives estimates of the percent change in the mean outcome corresponding to a change in the independent variable.

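### Each site PI performs the within-site block randomisation in a trial with visibly different arms, and the plan describes nothing that conceals the next allocation

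*Combined protocol and SAP*

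**What the plan says.** The Baseline Visit (V0) text in section 4f assigns the task: "Each site PIs will perform the baseline growth assessment and perform randomization at time of enrollment". The next sentence gives the method: "We will perform block randomization to ensure equal distribution within each site". Section 5c repeats it: "We employed a block randomization design for each site to ensure balanced distribution of treatment groups". Neither place says how large the blocks are, whether they vary, who generates or holds the sequence, or how the next assignment is hidden.

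The arms are visibly different. Under Study Procedures, "Infants randomized to utilization of RHO will receive a Masimo Rad-8 pulse oximeter and serial data recorder", and Arm B families send in data every 4 to 7 days. Arm A infants have a polysomnogram before oxygen is stopped (section 4.d). No masking of site staff is described.

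The role that randomises has other duties. At BCH, section 4c says "The site PI will review the NICU census at BWH and BIDMC once per week", partly "to determine if there are contraindications to approaching families". The Informed Consent text lets the site PI or the study team take consent there. Section 4a adds, for all sites: "Duration of HOT therapy for each arm of the study will be documented by each site investigator". That duration is a primary outcome.

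REDCap appears only as a data system. Section 4f introduces it for the coded identifier, "which will be used in a RedCap database to preserve confidentiality". UMass is named as coordinating centre (section 4c) but is given no part in allocation.

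**The concern.** Randomisation protects a comparison only if nobody who can influence enrolment knows which arm comes next. In a blocked design with visible arms, a site can see its own past allocations and work out which arm is behind. If the person who randomises also has a say in whom to approach and when, infants expected to wean quickly could be enrolled when one arm is due and others deferred. No bad intent is needed.

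Duration of home oxygen is the outcome most exposed. Sections 5c and 5d compare it between groups by means, without adjustment. Covariate adjustment is specified only for the PedsQL analysis.

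**Working it through.** The plan states no block size or predictability figure, so there is nothing of its own to reproduce. The check asks how predictable allocation would be over a range of block sizes.

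**Inputs**
- 196 infants at 9 centres, 68 of them at BCH (Abstract). The other eight centres average (196 − 68)/8 = 16.
- Equal allocation, blocked within site (sections 4f and 5c).
- Target difference of 36 days (section 5d).
- Block size b: not stated. Assumed to be 2, 4, 6 or 8.

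**Step 1: allocations fixed by earlier ones.** This assumes that b is constant and known, and that past allocations are tracked. Once one arm's places in a block are used up, the rest of the block is certain. Averaged over all balanced sequences, the determined share is 2/(b + 2). For b = 4 there are 6 sequences and 24 allocations. Two sequences (AABB, BBAA) have the last two places fixed and the other four have only the last: 2×2 + 4×1 = 8, and 8/24 = 1/3.

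**Step 2: chance of a correct guess.** The rule is to guess the arm that is behind and toss a coin when the arms are level. For b = 4, a sequence such as AABB scores 0.5 + 0 + 1 + 1 = 2.5, while ABAB and ABBA each score 0.5 + 1 + 0.5 + 1 = 3. The average is 8.5/12 = 71%. This rule does not require knowing b.

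| Assumed b | Determined share | Of 196 | Of 68 at BCH | Correct guess |
|---|---|---|---|---|
| 2 | 50% | 98 | 34 | 75% |
| 4 | 33% | 65 | 23 | 71% |
| 6 | 25% | 49 | 17 | 68% |
| 8 | 20% | 39 | 14 | 67% |

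Guessing without information would be right 50% of the time. The counts assume complete blocks and are approximate otherwise. With b = 6, for example, 68 infants make 11 full blocks with 2 left over.

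**Step 3: what it could do to the primary outcome (illustration only).** Suppose that infants enrolled when one arm is guessed differ by g days in expected duration from those enrolled when the other is guessed. If every guess is acted on, the bias in the mean difference is g × (2p − 1), where p is the chance of a correct guess. With an assumed g = 20:
- b = 2: 20 × 0.500 = 10.0 days
- b = 4: 20 × 0.417 = 8.3 days
- b = 6: 20 × 0.367 = 7.3 days
- b = 8: 20 × 0.332 = 6.6 days

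Against the 36-day target this is 18% to 28% (6.6/36 to 10/36). Both g and full use of every guess are assumptions.

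**Step 4: what varied blocks leave behind.** Expected correct guesses per block are 1.5 (b = 2), 2.83 (b = 4) and 4.1 (b = 6). Mixing sizes 2 and 4 equally gives (1.5 + 2.83)/6 = 72%. Mixing 4 and 6 gives (2.83 + 4.1)/10 = 69%. Simulation to 68 infants gave 72% and 69%. Varied, undisclosed sizes remove certainty but not above-chance guessing.

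**The case against.** The strongest reply is that this is a silence, not a demonstrated fault. Performing randomisation could mean requesting a central assignment or opening a sealed envelope, and a concealed system cannot be ruled out. No section says that blocks are fixed, and certain prediction needs a fixed size that the site knows. That stands. A reader might infer that allocations were in fact predictable, but the documents do not show it.

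A reader might also infer that the site PI alone decides eligibility and runs weaning. The text does not support this. No section says who judges eligibility. The screening and approach role is described for BCH only, and consent is shared with the study team. Clinic staff run the Arm A challenge, Arm B recordings go to UMass for analysis, and both arms follow the Table 1 thresholds.

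Some text does limit the room to steer. Recruitment is to be sequential (section 4b) and done by research assistants (section 4c). The NICU team determines the oxygen requirement, most exclusions are objective, and eligibility and consent come before the baseline procedures. These are real constraints, but none hides the next allocation from the person who randomises.

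Finally, severity and demographic variables are collected under Control for Confounding Variables, so it would be too strong to say that no analysis could help. Adjustment could reduce measured imbalance. It could not remove selection on what the investigator saw but nobody recorded.

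**Conclusion.** The point holds as a design weakness. The plan names the site PI as the person who randomises, uses within-site blocks with visible arms, and describes no safeguard that conceals the next assignment. That goes beyond a missing detail, because the one step that is specified is the one best moved away from the site.

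Its size depends on an unstated block size. If blocks were fixed and known, between a half (blocks of 2) and a quarter (blocks of 6) of allocations would be certain in advance, or about 98 to 49 of 196. These count predictable allocations, not steered infants. The bias of about 7 to 10 days is an illustration under an assumed 20-day difference and full exploitation. That site staff are unmasked is inferred from the differences between the arms, since the text does not say so. Nothing in the documents indicates that steering took place.

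**What to change.** In section 4f (Baseline Visit) and section 5c, replace randomisation by the site PI with central allocation by the coordinating centre, for example through the REDCap database if it supports this. Specify:
- who generates and holds the sequence;
- randomly varied block sizes within site, not disclosed to sites;
- release of each allocation only after eligibility, consent and the baseline growth assessment are recorded.

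Obtain the baseline PedsQL before release where possible. Section 4f allows it to be completed by phone after the visit, when the parent may already know the arm, so the two provisions need to be aligned. A log of screened infants with reasons for non-enrolment would help to show whether selection occurred.

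The costs are database set-up, protocol wording and slightly more imbalance within sites. The sample size is unchanged. There are two limits. Guessing stays above chance (about 69% to 72%), as it would in any unmasked blocked design. The change also reaches only infants not yet randomised, and section 4.d already refers to participants who have completed the study. For those infants, document how allocation was actually done. If a concealed system was already in use, describing it in the plan settles that part of the point.
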